## LIST OF ABBREVIATIONS AND RELEVANT DEFINITIONS

AE	Adverse Event
BIA	Bioelectrical Impedance Analysis
BMI	Body Mass Index
CCMO	Central Committee on Research Involving Human Subjects; in Dutch: Centrale Commissie Mensgebonden Onderzoek
DSMB	Data Safety Monitoring Board
EPR	Electronic Patient Record
ESPEN	European Society of Parenteral and Enteral Nutrition
FM	Fat Mass
FFM	Fat-Free Mass
GCP	Good Clinical Practice
GDPR	General Data Protection Regulation; in Dutch: Algemene Verordening Gegevensbescherming (AVG)
IC	Informed Consent
METC	Medical research ethics committee (MREC); in Dutch: medisch-ethische toetsingscommissie (METC)
MNA	Mini Nutritional Assessment
MUST	Malnutrition Universal Screening Tool
ONS	Oral Nutritional Supplements
PG-SGA- (SF)	Patient Generated Subjective Global Assessment (Short Form)
Review Committee	Medical research ethics committee (MREC) or CCMO
RCT	Randomized Controlled Trial
RNIT	Randomized Controlled Non-Inferiority Trial
(S)AE	(Serious) Adverse Event
SNAQ	Short Nutritional Assessment Questionnaire
SPPB	Short Physical Performance Battery
Sponsor	The sponsor is the party that commissions the organisation or performance of the research, for example a pharmaceutical company, academic hospital, scientific organisation or investigator. A party that provides funding for a study but does not commission it is not regarded as the sponsor, but referred to as a subsidising party.
SQUASH	Short Questionnaire to Assess Health-enhancing physical activity
TUG	Timed Up and Go

UAVG	Dutch Act on Implementation of the General Data Protection Regulation; in Dutch: Uitvoeringswet AVG
WHO	World Health Organization
WMO	Medical Research Involving Human Subjects Act; in Dutch: Wet Medisch-wetenschappelijk Onderzoek met Mensen

## SUMMARY

**Rationale:** Risk of malnutrition is a common condition in hospitalized patients, with a prevalence up to almost 40% depending on the specific patient population. As part of the dietary counseling, oral nutritional supplements (ONS) (i.e., energy and protein-rich drinks) are advised when habitual oral nutritional intake remains inadequate (75% of protein and energy requirements). ONS are effective in increasing total energy and protein intake, resulting in less complications and re-admissions, as well as improved body weight and physical functioning.

Recently the Dutch Ministry of Health, Welfare and Sport and the Dutch Federation of University centers signed the Green Deal “Working together on sustainable care” in which they agreed on “Green and climate neutral care” by 2026. This also includes meeting criteria for purchasing medical and non-medical nutrition in hospitals for future tenders.

The development of ONS transitioning towards more plant-based proteins already receives much attention, which is deemed relevant in terms of overall sustainability. However, so far no studies have investigated the effectiveness of long-term use of plant-based ONS on an adequacy of protein and energy intake, nutritional status, muscle status, as well as physical and clinical outcomes. Hence, further research is needed to address the knowledge gaps on effectiveness of plant-based ONS. Yet, before conducting a randomized controlled trial (RCT), it is essential to first assess the feasibility of such a study in terms of patient recruitment, drop-out rates, adherence, and feasibility of study measurements. The current protocol describes this pilot feasibility, the results of which will provide essential insights to subsequently setup a study protocol for a full scale RCT to address effectiveness of plant-based ONS vs (traditional) animal-based ONS. Thus, this pilot feasibility study aims to assess the feasibility of a multicenter randomized controlled non-inferiority trial (RNIT) to compare plant-based ONS versus animal-based ONS.

**Objective:** The primary objective of this study is to investigate the feasibility (patient recruitment, drop-out rate, adherence, and study measurements) of a multicenter RNIT comparing plant-based versus animal-based ONS. The secondary objective of this study is to evaluate the energy and protein intake versus requirements, nutritional status, muscle status, physical and clinical outcomes, and patient's satisfaction with long-term supplementation.

**Study design:** A multicenter pilot randomized feasibility study

**Study population:** Patients from the medical oncology, lung diseases, cardiology, cardiothoracic surgery, and orthopaedic departments at risk for inadequate nutritional intake treated at Maastricht UMC+ and Radboudumc.

**Intervention (if applicable):** the intervention group receives plant-based ONS (Fresubin® Plant-based Drink vanilla) and the control group receives animal based ONS (Fresubin® Yodrink raspberry) during hospital admission/treatment and up to 3 months after.

**Main study parameters/endpoints:** The primary endpoint of the study is the feasibility of the RNIT with respect to the recruitment, drop-out, adherence, and study measurements.

**Nature and extent of the burden and risks associated with participation, benefit and group relatedness:** This study will not cause much additional burden on the patients in addition to their normal treatment as measurements are carried out during their hospital admission, or when possible, they are already present in the hospital for another appointment at the outpatient clinic. There will be two moments where measurements will be performed. The additional time needed to performing the measurements of this study will be approximately 90 minutes, both at the start and at the end of the intervention period. After one and after two months, a short 'check-in' will be done (phone call or at the hospital if patient has appointment there), this takes approximately 10 minutes.

The participants are asked to perform 3 physical tests and complete questionnaires, which could be experienced as exhausting/ a burden. There are no further risks associated with this research. Patients will not perceive direct benefits from participation in this study. It is expected that the use of ONS will increase energy and protein intake of the participants, which in turn could improve their nutritional status.

## 1. INTRODUCTION AND RATIONALE

Risk of malnutrition is highly prevalent in hospitals, with prevalence rates up to almost 40% on hospital admission, depending on the specific patient population (1-3). Especially in oncological, surgical and elderly patients, malnutrition is very common with reported prevalence ranging from 21% of severe risk on malnutrition up to even 40% in specific cancer types such as head and neck, gastrointestinal, lung, ovarian and urological cancer (4,5) and up to 66% in older patients in acute care and rehabilitation (6). Malnutrition is associated with poor physical functioning, impaired wound healing, complications, prolonged duration of hospitalization, lower quality of life and increased mortality (7-9). In the Netherlands, the additional health care costs associated with malnutrition are estimated at an annual € 1.8 billion (10). Given its prevalence and the associated negative health consequences, the Dutch Inspectorate of Health and Youth has included 'Malnutrition' in the "Basic set of medical specialist care" as a target for improvement for 2023 and beyond. The objective for improvement described in this Basic set is to diagnose and treat malnutrition in an early phase before, during and/or after hospitalization, while also giving special attention to continuation of treatment after discharge, in the home situation (11). In all Dutch hospitals, patients should be screened for malnutrition upon hospitalization (MUST  $\geq 2$ /SNAQ  $\geq 3$ /PG-SGA-SF  $\geq 9$ ).

Throughout hospitalization, food intake of patients is often inadequate, due to reduced appetite and disease impact symptoms, such as pain, nausea, decreased taste and smell (12). Adding further complexity to this problem, nutritional requirements are increased due to illness, treatment and the healing process. As such, it can be challenging to adequately meet the nutritional requirements during the course of hospitalization and rehabilitation. Patients at risk of malnutrition will receive individual counseling by a dietitian, aimed at reaching adequate protein and energy intake. As part of this nutritional counseling, oral nutritional supplements (ONS) (i.e., energy and protein-rich drinks) are advised when habitual oral nutrition remains inadequate (75% of protein and energy requirements) (13). ONS are effective in increasing total energy and protein intake, resulting in less complications and re-admissions, as well as improved body weight and physical functioning (14). Currently available ONS mostly contain animal-based proteins, usually in the form of dairy proteins, ensuring high-quality proteins with regard to digestibility, amino acid composition, and bioavailability.

Recently the Dutch Ministry of Health, Welfare and Sport and the Dutch Federation of University centers signed the Green Deal "Working together on sustainable care" in which they agreed on "Green and climate neutral care" by 2026. One of the five goals is to stimulate "a healthy, varied, more plant-based and sustainable diet" (15). This also includes

meeting criteria for purchasing medical and non-medical nutrition in hospitals for future tenders.

Already much attention is given to replacing part of the animal-based protein in hospital diets with plant-based protein sources, which is deemed relevant in terms of overall sustainability as well as enabling to feed the ever-growing world's population (16). Although in general, plant-based proteins are assumed to be of less nutritional value (e.g., less complete amino acid profile, lower digestibility), more and more options are being developed to improve the bioavailability and nutritional value of more sustainable, plant-based proteins, thereby supporting their use to meet specific protein and amino acid requirements. For example, various legumes such as soy, lentils, and pea, and/or (combinations of) wheats and nuts, and even insect proteins have been suggested as alternative protein sources. The first studies in young, healthy adults even confirm that ingestion of an ample amount of (combinations of) such plant-based proteins can induce a similar anabolic response as compared to high-quality milk protein (17). One of the important factors that drives the anabolic response to protein ingestion is the essential amino acid content of the protein with leucine being of particular importance (18). In this respect, soy protein is traditionally viewed as a relevant plant-based protein source due to its excellent digestibility as well as its relatively high essential amino acid content (27%) and leucine content (19). Although soy protein supplementation has been suggested as a promising strategy for maintaining muscle mass and function in older people, the more long-term effects in both healthy and more compromised (clinical) populations remain to be established (20).

The transition towards more plant-based ONS already receives much attention. However, it is unknown whether patient satisfaction (e.g., taste, smell, satiety, opinion) of plant-based ONS is similar compared to regular animal-based products. Moreover, so far the effectiveness of plant-based ONS to support adequate protein and energy intake, nutritional status, muscle status, as well as physical and clinical outcomes with long-term supplementation has not been investigated. Hence, further research is needed to address these knowledge gaps. However, before conducting a randomized controlled trial (RCT), it is essential to first assess the feasibility of such a study in terms of patient recruitment, drop-out rates, adherence, and feasibility of study measurements. The current protocol describes this pilot feasibility study, the results of which will be used to setup the study protocol for full scale RCT. This pilot feasibility study aims to assess the feasibility of a (subsequent) multicenter randomized controlled non-inferiority trial (RNIT) to evaluate energy and protein intake versus requirements in patients with cancer and lung diseases, cardiology patients, patients with cardiothoracic surgery, and orthopaedic patients at risk for inadequate nutritional intake when using plant-based or animal-based ONS.

## 2. OBJECTIVES

### **Primary Objective:**

The primary objective of this study is to investigate the feasibility (patient recruitment, drop-out rates, adherence, and study measurements) of a multicenter RNIT comparing plant-based versus animal-based ONS in patients with cancer and lung diseases, cardiology patients, patients with cardiothoracic surgery, and orthopaedic patients at risk for inadequate nutritional intake.

### **Primary research question:**

What is the feasibility of a multicenter RNIT comparing plant-based ONS versus animal-based ONS in patients with cancer and lung diseases, cardiology patients, patients with cardiothoracic surgery, and orthopaedic patients at risk for inadequate nutritional intake with respect to the patient recruitment, drop-out rates, adherence, and study measurements?

### **Sub-questions:**

#### Recruitment:

- What is the recruitment rate?
- What are characteristics of included and excluded patients (per patient group)?

#### Drop-out:

- What is the drop-out rate (percentage of patients that dropped out)?
- At what time points in the study (week number after inclusion) do patients drop out?
- What are reasons for dropping out?

#### Adherence:

- What is the percentage of ONS consumed versus advised?
- What are the reasons of not filling out questionnaires?

#### Study measurements:

- What is the percentage of successfully performed measurements?
- What are reasons for unsuccessful measurements?

### **Secondary Objective(s):**

To assess the energy and protein intake, nutritional status, muscle status, physical and clinical outcomes, and patient's satisfaction of long-term use of ONS.

**Secondary research questions:**

1. What is the energy and protein intake in patients receiving plant-based ONS with patients receiving animal-based ONS?
2. How do nutritional status, muscle mass status, physical and clinical outcomes differ between patients using plant-based ONS compared to patients using animal-based ONS?
3. How are the plant-based ONS and animal-based ONS evaluated regarding patients' satisfaction (taste, smell, satiety), their wishes and needs, and their opinion about sustainable nutrition?

**3. STUDY DESIGN**

This study is a pilot randomized feasibility study in patients with cancer and lung diseases, cardiology patients, patients with cardiothoracic surgery, and orthopaedic patients at risk for inadequate nutritional intake to evaluate feasibility and patient satisfaction necessary to determine a suitable patient population and calculate the sample size for a larger RNIT (i.e. study 2). In study 2, a large RNIT will be conducted to establish the long-term efficacy of plant-based vs animal-based ONS. During this pilot study, patients who are advised ONS according to usual care and signed informed consent (IC) will be randomized to receive either plant-based ONS or animal-based ONS. Several measurements will be performed at 0 and 3 months. A total of 60 patients will be included. The main aim is to establish the feasibility in terms of recruitment, drop-out rate, adherence, and study measurements of the different subpopulations, reflecting feasibility for performing study 2. Furthermore, we will collect data on protein and energy intake, which will be used for the sample size calculation of study 2. Apart from the quantitative measurements, study 1 will also be setup as a qualitative study to determine patients' satisfaction, wishes and needs towards the ONS. Data on patients' satisfaction will only be used as observational data, no comparison between the two types of products will be made.

Measurements will be performed during hospital admission, or before/after an already scheduled appointment at the hospital outpatient clinic (baseline T0), and three months after baseline (T3). Within these 3 months, patients will be contacted by the researcher 1 month after the start (T1) and 2 months after the start (T2) for a 'check-in' conversation. For this conversation the researcher will either make a phone call or have brief conversation at the

hospital if the patient is already there for another appointment. The researcher will ask about any changes in body weight, discuss changes in the nutritional advice provided by the dietitian, ensure the patient is still correctly filling out the logbook, and address any questions or concerns related to the study. The study will be conducted at Radboud university medical center (Radboudumc) in Nijmegen, the Netherlands, and Maastricht University Medical Center (Maastricht UMC+) in Maastricht, the Netherlands.

## 4. STUDY POPULATION

### 4.1 Population (base)

The study population will consist of patients with cancer and lung diseases, cardiology patients, patients with cardiothoracic surgery, and orthopaedic patients at risk for inadequate nutritional intake treated at Radboudumc or Maastricht UMC+.

### 4.2 Inclusion criteria

In order to be eligible to participate in this study, a participant must meet all of the following criteria:

- Clinical patients with cancer and lung diseases, cardiology patients, patients with cardiothoracic surgery, and orthopaedic patients age  $\geq 18$  years, and treated at Radboudumc or Maastricht UMC+.
- Patients who have been advised at least 2 bottles of ONS daily based on their nutritional requirements.
- Written informed consent (IC)

### 4.3 Exclusion criteria

A potential participant who meets any of the following criteria will be excluded from participation in this study:

- Patients who are or become dependent on tube or parenteral nutrition
- Patients where life-extending therapy is no longer possible
- Unable to follow up study instructions
- Lactose intolerance
- Soy allergy/intolerance
- Vegan diet
- Patients who have used ONS in the past six months

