### 8.3 Study procedures

Measurements during this study will be combined as best as possible during appointments planned within routine care at the hospital. Baseline measurements will take place at the start of the ONS treatment (T0) during hospital admission or during an appointment at the outpatient clinic. 1 month after the start (T1) and 2 months after the start (T2) the researcher will have a brief 'check-in' via a phone call or a conversation at the hospital if the patient is there for another appointment. 3 months after initiation (T3) the same measurements will be performed as at baseline (T0). In addition, at T3, the researcher will conduct an interview about patients' satisfaction about the ONS (Table 1).

Table 1: Overview of the study measurements for each time point.

Measurements	Treatment initiation (T0)	1 month after initiation (T1)	2 months after initiation (T2)	3 months after initiation (T3)
Body height, body weight, usual body weight, BMI	X	X	X	X
Nutritional intake (protein and energy)	X			X
Compliance ONS	X	X	X	X
Check-in conversation		X	X	
Nutritional status (PG-SGA, fat mass and fat-free mass, and muscle thickness)	X			X

Hand grip strength	X			X
Physical Activity (SQUASH)	X			X
Physical performance (TUG, SPPB)	X			X
Quality of life (EORTC-QoL-C30) and Clinical outcome measures (length of hospital stay, complications, readmission and mortality)	X			X
Patient's satisfaction about the Oral nutritional supplements				X

Body height, body weight, BMI are measured on a calibrated scale and stadiometer. Usual body weight will be asked. During the check-in process, patients are required to weigh themselves either at home or at the hospital, if they have another appointment scheduled there.

Nutritional intake and compliance of oral nutritional supplements used during hospital admittance will be measured by food registration in the Electronic Patient Record (EPR) registered by the nutritional assistant with a cross-check of a nutritional researcher.

Additionally, the researcher will also ask if there are any variations in their food intake on bad versus good days and whether there have been any changes in eating habits compared to a month ago. Patients who are not admitted to hospital but come to the hospital on an outpatient basis, are being asked to fill out a 3-day food diary (2 week days and 1 weekend day). After 3 months the all patients will all fill out a 3-day food diary. During the 3 months,

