### **8.4.1 Specific criteria for withdrawal (if applicable)**

Not applicable

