## **8.6 Follow-up of research participants withdrawn from treatment**

Not applicable

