### **10.2 Secondary study parameter(s)**

Secondary analysis will provide the mean difference in protein intake i.e., total protein intake in g/kg FFM/d (based on dietary history) divided by 1.5-1.9 g/kg FFM/d, times 100%. In addition, the mean difference in energy intake i.e., total energy intake in kcal/d (based on dietary history) divided by WHO formula + surcharge up to 50%, times 100%. ANCOVA analysis will be used to estimate the effect of the group as independent factor on 'mean difference in intake vs recommendation' at T3 as dependent variable and T0 measurement as covariate. This is only meant as exploratory analyses and to be used for sample size calculations for the subsequent full-scale RCT.

The aim of the semi-structured interviews is to understand the experiences and perspectives of the patients using ONS regarding satisfaction (taste, smell, satiety), as well as their wishes and needs. Additionally, we are interested in their views of

sustainable nutrition. Therefore, these interviews will be approached from a phenomenological perspective. Qualitative analysis: all interviews will be audiotaped, and the records will be transcribed verbatim. Data will be analyzed using thematic analysis, starting with initial open coding to identify relevant data by minimal two independently working researchers. Codes will then be grouped into categories, the axial codes, and overarching themes will be identified. For this analysis, the software Atlas.ti will be used.

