approach the patient to ask whether they are interested in receiving more information about the study from the researcher. The researcher will contact the patient as soon as possible. In this (phone) conversation the researcher further explains the study, and the patient can ask his/her questions. After this conversation the patient has 24 hours to decide if they want to participate or not. During this time, the patient will have the opportunity to consider their participation. If additional time is required for decision-making, this will be accommodated. Because the patient is at risk for inadequate nutritional intake, it is important that after the dietitian has advised the ONS, the patient also receives the drinks within a short period of time. That is why it is essential that we randomize the patient into one of the groups after 24 hours. If the patient is willing to participate, an appointment is made for the IC procedure. The IC form will be provided by the researcher and will be signed in a private room, prior to study initiation. Confidential processing of data and anonymity are guaranteed. Participants will have the opportunity to withdraw from the study at any time without the need to provide a reason.

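### Section 4.3 excludes patients who become tube- or parenteral-dependent, which read literally is a post-randomisation withdrawal rule that 8.4.1 denies and for which 8.6 gives no follow-up

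*Protocol*

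**What the plan says.** Protocol section 4.3 opens its list with "A potential participant who meets any of the following criteria will be excluded from participation in this study". The first item is "Patients who are or become dependent on tube or parenteral nutrition". It is the only item in the list worded for a future state.

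The sections on withdrawal and follow-up say little:

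- **8.4** gives two routes out: the participant's own wish, or the investigator's decision for urgent medical reasons.
- **8.4.1**, on specific withdrawal criteria, is answered in full by not applicable.
- **8.5** says that withdrawn participants are not replaced, because recruitment and drop-out are themselves key feasibility measures.
- **8.6**, headed "8.6 Follow-up of research participants withdrawn from treatment", is also answered in full by not applicable.

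Section 8.3 plans the final assessment without any condition on continued supplement use: "3 months after initiation (T3) the same measurements will be performed as at baseline (T0", and "After 3 months the all patients will all fill out a 3-day food diary".

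Drop-out is one of the four components of the primary endpoint (8.1.1). Sections 3 and 10.2 both say that the intake data will feed the sample size calculation of the next, full-scale trial.

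**The concern.** Starting tube or parenteral feeding is what may happen when oral intake fails, so it is close to the outcome that the intake analysis measures. A rule that removes patients at that moment selects on outcome after randomisation. If no follow-up is attached to it, T3 intake, body composition and function are never measured, and no later analysis plan can recover them.

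Two things are at stake. First, stopping the supplement and leaving the study become one event, although the planners of study 2 need to know them separately: the first concerns the product and the patient's condition, the second whether outcomes can be collected. Second, the T3 intake data for sizing study 2 would lack the patients whose oral intake failed. Two sites must apply the rule, and section 12.2 says there will be no monitoring, so different handling at the two sites could pass unnoticed.

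**Working it through.** **Step 1: the sections side by side.** The plan states no figure on this point; the check is one of consistency.

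| Question | Where | Answer |
|---|---|---|
| Is a patient already dependent at screening excluded? | 4.3 | Yes, by *are* |
| Is a patient who becomes dependent later excluded? | 4.3 | Yes, read literally, by *or become* |
| Is there a specific withdrawal criterion? | 8.4.1 | Not applicable |
| What follow-up applies after stopping treatment? | 8.6 | Not applicable |
| Who has T3? | 8.3 | All patients, with no condition on supplement use |
| Does starting tube or parenteral feeding count as drop-out? | 2, 8.5, 10.1 | Not stated |

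The word *are* already covers dependence at screening, so *or become* has to add something.

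- If it adds the period after randomisation, 4.3 acts as a withdrawal criterion, against 8.4.1, and with 8.6 as written nothing requires T3.
- If it adds only the interval between the supplement advice and randomisation, there is no conflict, but a randomised patient who later starts tube or parenteral feeding is still not expressly dealt with.

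Neither reading gives a site an explicit rule for such a participant.

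**Step 2: effect on the drop-out rate.** Inputs from section 4.4: 60 patients, 30 per group. Each patient whose status changes from retained to drop-out moves the rate by

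- overall: 1/60 = 1.7 percentage points;
- within one arm: 1/30 = 3.3 percentage points.

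**Step 3: illustration.** The protocol gives neither an expected drop-out rate nor a rate of tube or parenteral feeding. Assume 12 of 60 drop out for other reasons and k further patients become dependent.

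| k (assumed) | Counted as drop-outs, (12 + k)/60 | Kept to T3, 12/60 | Removed from the denominator, 12/(60 − k) | With T3 data if excluded, 48 − k |
|---|---|---|---|---|
| 3 | 25% | 20% | 21.1% | 45 |
| 6 | 30% | 20% | 22.2% | 42 |
| 9 | 35% | 20% | 23.5% | 39 |

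If they are kept and attend, 48 have T3 data. The gap between the second and third columns is k/60, whatever number is assumed for other drop-outs. For scale, exact 95% intervals are 10.8% to 32.3% for 12/60 and 18.8% to 43.2% for 18/60. They overlap widely, so the ambiguity adds to an estimate that is already imprecise.

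**Step 4: effect on T3 intake.** No size or direction follows from the protocol. The effect depends on how many patients are affected, on whether tube or parenteral feeding counts in "total protein intake in g/kg FFM/d (based on dietary history"), and on whether study 2 will itself keep such patients. The first is unknown, and the protocol does not settle the other two.

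**The case against.** The strongest defence is that the text can be read without conflict. The list in 4.3 governs potential participants. Section 11.2 says "After this conversation the patient has 24 hours to decide if they want to participate or not", with more time if needed, so *become* can be taken to cover that interval only. Section 8.4 then gives the withdrawal routes, 8.4.1 adds none, and 8.3 makes T3 the default for all. This reading is fair, and for that reason the point is about ambiguous text. A reader might infer that the protocol plans to drop these patients; it does not say so, and the lead-in to 4.3 and the wording of 8.3 both tell against it. What the defence leaves standing is that 4.3 can be applied to randomised patients, and 8.6, the section meant for that case, is left empty.

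There are also safeguards. Section 2 asks for the week of and reasons for drop-out, and the reasons for unsuccessful measurements. Section 8.3 takes length of stay, mortality, readmissions and complications wholly or partly from the patient record. Departures for tube feeding should therefore be visible, and not every outcome hangs on a T3 visit. But recording why a patient left does not supply the missing T3 intake, body composition or function.

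A reader might also infer that the T3 mean and standard deviation will be biased in a known direction, or by an amount that would mis-size study 2. The documents do not support that. The intake analysis is labelled exploratory, and if study 2 also stops at tube feeding, a standard deviation without these patients could be the relevant one. How tube feeding enters the intake derivation, and who enters the analysis set, may properly be settled in an analysis plan that is not shown. Whether a participant is withdrawn and whether T3 is attempted are rules of conduct, and those belong in the protocol.

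**Conclusion.** The point holds as a minor one. Read literally, 4.3 removes randomised participants for an outcome-related reason, contradicts 8.4.1, and leaves them without follow-up under 8.6, although 8.3 plans T3 for all. On the entry-only reading the contradiction goes, but the protocol still has no explicit rule for them.

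The demonstrable consequence is for the primary endpoint: 1.7 points of overall drop-out, or 3.3 points in one arm, for each patient handled one way rather than the other. This uses only the planned 60 and 30; how many patients would be affected is not known. Loss of T3 data intended for study 2 is a real possibility under the literal reading, of unknown size and direction. No type I error rate, power figure or sample size in the protocol is affected, since the 60 is a convenience sample.

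**What to change.** 1. In 4.3, replace the item with: *are dependent on tube or parenteral nutrition at randomisation*. Checking status at that moment still screens out a candidate who becomes dependent while deciding.
2. In 8.6, replace the present answer with: *participants who stop ONS, including those who start tube or parenteral feeding, remain in the study and T3 measurements are sought unless consent is withdrawn*.
3. Report stopping the supplement separately from study drop-out.
4. At T3, note oral intake and tube/parenteral intake separately, so that study 2 can be sized with or without these patients.

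If the sponsor does intend withdrawal, 8.4.1 should say so and state how these patients count towards drop-out; the retention wording above is preferable because it keeps the data.

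The cost is two changes of wording, one extra line of reporting, a little more intake recording, and a few T3 visits of about 90 minutes (11.4) in ill patients, some of whom will not complete the physical tests. How patients are fed does not change.
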